#### **Randomization:**

Participants will be randomized to a study arm using a computer-generated randomization model prepared by the study biostatistician, to assign participants 1:1 across both study arms (THOR3 training + sham PBMT, or THOR3 training + PBMT).

#### **Study Treatments (THOR3 training + sham PBMT, THOR3 training + PBMT):**

Participants will be blinded to the study arm they are assigned to and will be unblinded at the conclusion of the final study visit.

Participants will be asked to refrain from using perfumes or plant extracts (e.g., St John's Wort) in the treatment areas, as this use can increase photosensitivity.

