#### **Recruitment, Pre-Screening (before consent), Study Introduction & Informed Consent:** Potential participants will be identified via three methods:

1. Participants may self-refer to participate in the study if they become aware of the study by study flyer (Appendix P) or word of mouth. Interested potential participants will be able to contact a member of the study team via phone or email.
2. Mass briefs at THOR3 coach-lead trainings.
  - Briefings will occur at regular intervals, about every 3 weeks, for each training class at the 3 Operator focused training sessions. In the course of a month, there will be about 4 briefings.
  - Briefings will take no more than five (5) minutes. The briefs will be scheduled to occur prior to the coach led session. Consenting procedures will not occur during these informational briefs.
  - Leadership would only include the OIC of THOR3, not Group Leadership. Every effort will be made to ensure there is not undue coercion.

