#### 3-Week Follow-Up:

Participants will follow-up with a study team member for a final study visit to:

- turn in the final activity log and Oura Ring,
- be assessed for any adverse events (AEs),

- complete CMJ and lower body strength assessments,
- complete a follow-up questionnaire, and
- be unblinded to their study treatment.

Participants will not be held responsible for lost or damaged Oura Rings.

Study participation will end after the completion of the 3-week follow-up visit.

Data may be captured in-person or remotely (e.g., entered directly into REDCap using a personalized coded link with no log-in required, verbally over the phone with a study team member, etc.), as applicable. Reminder phone calls, texts, and/or emails will be sent to participants at their preferred contact method indicated on the Intake CRF (Appendix B).

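### Telling each participant his arm at his own last visit, while others in the same training classes are still being recruited and treated, puts the participant blind at avoidable risk; holding disclosure to the end is a cheap improvement.

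*Combined protocol and SAP*

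**What the plan says.** **Disclosure.** Section 10.1, Study Treatments, keeps participants unaware of their arm during the study and states that they "will be unblinded at the conclusion of the final study visit". The 3-Week Follow-Up list in the same section has each participant "be unblinded to their study treatment" as its last item, after the jump and strength tests and the questionnaire. It adds: "Study participation will end after the completion of the 3-week follow-up visit". Disclosure is therefore per participant and is not tied to the end of the trial.

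**Recruitment.** All activity takes place within one Special Forces Group at one base (10.1, opening paragraph). The recruitment text says: "Briefings will occur at regular intervals, about every 3 weeks, for each training class at the 3 Operator focused training sessions". It continues: "In the course of a month, there will be about 4 briefings". Men may also self-refer "if they become aware of the study by study flyer (Appendix P) or word of mouth". All participants train in the same coach-led programme (10.1, THOR3 Coach-Lead Training).

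**Treatment and masking.** Treatment is given up to three times a week for three weeks. All participants wear blackout glasses and headphones. For sham, the device stays in standby and emits nothing (10.1, Sham PBMT Arm). Section 14.1 says that mild discomfort may occur, asks participants to report uncomfortable warming, and calls uncomfortable skin heating very rare.

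**Blinding and outcomes.** The design is single-blind (9.4), and participants are the only people described as blinded. Section 10.2 lists pain (DVPRS), soreness (VAS), Borg exertion and the Elloumi scale, which are self-reported, together with jump and dynamometer tests.

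**The concern.** The sham is there so that any difference between arms can be put down to light emission. That depends on participants not knowing which procedure they received. If active and sham feel different on the skin, a finisher who has been told his arm can label the sensation for others: a man who hears that active felt warm, and who feels nothing himself, has reason to think he is on sham. Without disclosure, men can compare sensations but cannot be sure which belongs to which arm.

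If beliefs then differ between arms, self-ratings of pain, soreness, exertion and fatigue can follow belief, and so can effort in jump and strength tests. The expected direction favours active treatment. Passive Oura Ring measures are less exposed.

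**Working it through.** The plan gives no figure for blinding or for bias, so there is none to reproduce. The check has three steps.

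**1. Does disclosure overlap with recruitment and treatment?** Each man's participation ends at about 3 weeks. Each class is briefed again about every 3 weeks, with about four briefings a month in total. Unless nearly everyone enrols at once, some finishers will know their arm while others are still to start or are in treatment. No accrual period is stated. Under uniform accrual over T weeks (assumed), the first disclosure comes about 3 weeks after the first enrolment, and the share enrolling after it is (T − 3)/T:

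| T (weeks, assumed) | Share | Of 116 |
|---|---|---|
| 6 | 3/6 = 50% | 58 |
| 12 | 9/12 = 75% | 87 |
| 26 | 23/26 = 88% | 103 |
| 52 | 49/52 = 94% | 109 |

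This counts men who start after any one participant has been told his arm. It does not count men who meet such a participant or learn anything from him, so it is a ceiling on exposure among later starters and not an estimate of it.

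**2. Is there something to pass on?** Sham has no emission, and section 14.1 allows that active treatment may be felt as warming. Glasses and headphones do not mask skin sensation. A cue is therefore possible, but its strength and frequency are not given.

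**3. What would a given bias do?** Inputs:
- analysed sample of 42 and 43 per arm (section 11.2);
- two-sided 5% test (section 11.6);
- outcome standardised to SD 1 and compared by a two-sample t test, as a stand-in for the planned models;
- added gap between arms in the share believing they are on active treatment, and an effect of that belief of 0.4 SD (both assumed, with no basis in the documents).

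Standard error = √(1/42 + 1/43) = 0.217 SD. Degrees of freedom = 42 + 43 − 2 = 83. Bias = gap × 0.4. Type I error is taken from the noncentral t distribution with noncentrality bias/0.217:

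| Added gap in belief (points, assumed) | Bias (SD) | Two-sided type I error |
|---|---|---|
| 0 | 0 | 5.0% |
| 5 | 0.05 × 0.4 = 0.02 | 5.1% |
| 10 | 0.10 × 0.4 = 0.04 | 5.4% |
| 25 | 0.25 × 0.4 = 0.10 | 7.4% |
| 50 | 0.50 × 0.4 = 0.20 | 14.9% |

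The gap that matters here is the increment caused by early disclosure, averaged over all analysed men. Nothing in the documents places that increment within the table.

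**The case against.** The strongest reply concerns mechanism. A peer's arm says nothing about one's own unless the two procedures feel different. The plan says they differ only in photon emission. The small amber lights are hidden by the glasses, and section 14.1 says treatment should not feel hot. This stands as a limit on the size of the effect. It does not remove the risk, because the same section provides for warming to be felt.

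Second, if a cue exists, each man can notice it himself over as many as nine sessions (3 × 3), and men treated at the same time can compare notes. Early disclosure is answerable only for what it adds. This stands in full: the whole belief gap cannot be charged to disclosure timing, and delaying disclosure is a partial remedy.

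Third, a reader might infer more than the text supports:
- **That every finisher is unblinded before the next cohort starts.** No cohorts are described, and briefings, flyers and self-referral allow staggered, overlapping starts.
- **That the word-of-mouth route shows treatment information passing between men.** That sentence concerns learning that the study exists.
- **That any loss of blinding must favour active treatment.** Wrong guesses, or similar errors in both arms, need not.
- **That final data may be collected after disclosure, because remote capture is allowed.** The plan places unblinding at the conclusion of the visit and lists it last. The remote-capture sentence does not say that questionnaires may follow it.
- **That participants are never asked to keep their experience to themselves.** The consent text and appendices are not available for review, so this cannot be concluded.

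Finally, section 11.5 describes the study as feasibility or pilot in nature. That lowers the stakes, but it gives no reason for immediate disclosure, and the documents offer none.

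**Conclusion.** The point holds as a low-cost improvement to the timing of disclosure. The documents establish that disclosure is per participant, that recruitment repeats in the same classes at one base, that sham emits nothing, that warming is possible with active treatment, and that skin sensation is not masked. Together these support a risk to the only stated blind, mainly for self-reported and effort-dependent outcomes. They do not show that the blind will fail.

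The size of the added bias cannot be estimated. The range of about 5.1% to 14.9% for type I error, for an added bias of 0.02 to 0.20 SD, is illustrative and rests wholly on the assumed belief gap and belief effect. The stronger reading, that most participants would be exposed and the error rate materially inflated, is not supported. Sample size and power figures are unaffected.

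**What to change.** Amend Study Treatments and 3-Week Follow-Up in section 10.1, and the matching consent wording, so that participants are told their arm only after the last participant's 3-week visit or at database lock. The means exist already: the Intake CRF holds contact details (10.1, Contact Information Data Collection), and the Master List is kept until study closure (10.14). The messages must go out before that list is destroyed.

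The cost is a short protocol and consent amendment, one message per participant, and a longer wait for men to learn their arm. Visits, treatment and sample size do not change. The change removes the added risk from early disclosure only. It does not address what a man feels during his own sessions, or comparison between men treated at the same time.

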#### THOR3 Coach-Lead Training

All participants will be enrolled in the THOR3 coach-lead training program as a standard daily exercise regimen, focusing on muscle strength, endurance, and stamina. This program will proceed without interference from the study. Activity during the THOR3 program will be documented (e.g., exercises, reps, etc.) on Appendix G THOR3 Training Program Log CRF. A study team member will export the training schedule from Bridge Athletic and will insert the information into Appendix G and ask the participant to confirm what training they completed.

#### Photobiomodulation Treatment (PBMT)

PBMT will be delivered at 40W. A member of the study team will use the quadriceps measurements of the treatment area to calculate the PBMT treatment time (approximately 5-20 minutes). PBMT treatment will be provided up to 3 times a week, for 3 weeks. Participants will be asked to engage in 3 sessions per week; however, due to operational demands, we understand that they may not be able to attend all sessions and will then aim to minimally have them attend 2 sessions per week.

PBMT will be provided by a trained study team member. Training for the PBMT will be conducted by a LightForce representative. PBMT will be delivered using the LightForce® XLi 40W device with the Smart Hand Piece technology, created by LiteCure, LLC/DJO (New Castle, DE) which has a built-in accelerometer in the hand piece that controls the speed of light delivery to the treatment area. The LightForce® XLi therapy laser is an FDA cleared device for the treatment of pain. The trained team members will use the Smart Hand Piece technology, which achieves effective treatments and improves dosing accuracy by assessing the operator's speed and providing real-time visual (red – amber – green light) and sensory feedback. The Smart Hand Piece is calibrated to shut-off when moving too slowly, and warn the operator when moving too fast by vibrating. (See LightForce Brochure). The therapy is delivered through a flexible optical fiber threaded through the hand piece, which contains a rolling glass massage ball. PBMT will be delivered at specified J/cm^2 and applied to the quadriceps area.

In order to facilitate participant blinding to their randomized study group, all participants (regardless of their assigned study group) will be asked to wear blackout glasses and headphones during their treatment.

#### Sham PBMT Arm:

Sham PBMT will be provided by a trained study team member. Sham PBMT will be delivered in the same manner as indicated for the PBMT process above, but the device will stay in standby mode (i.e., the treatment mode will not be turned on). As infrared light is invisible to the naked eye, the only visible difference between treatment and standby modes is the presence of a few tiny amber lights (these lights are on during treatment mode).

The inclusion of sham PBMT will ensure all participant treatment procedures remain the same, with the exception of emission of photons (active treatment), thus, allowing for contribution of any differences between groups to be credited to the use of PBMT.

#### **Follow-Up Data Collection:**

Follow-up data will be recorded on Appendix E Follow-up Data Collection CRF.

Regardless of study arm assignment, all participants will be asked to log their daily activity and pain (Appendix F Activity Log CRF) and wear the Oura Ring for 3 weeks.

#### Weekly Follow-Up:

Participants will follow-up with a study team member once a week to:

- turn in the activity log and Oura Ring data,
- be assessed for any adverse events (AEs),
- complete CMJ measurements just prior to THOR3 training session, and
- complete a DOMS questionnaire.

#### 3-Week Follow-Up:

Participants will follow-up with a study team member for a final study visit to:

- turn in the final activity log and Oura Ring,
- be assessed for any adverse events (AEs),

- complete CMJ and lower body strength assessments,
- complete a follow-up questionnaire, and
- be unblinded to their study treatment.

Participants will not be held responsible for lost or damaged Oura Rings.

Study participation will end after the completion of the 3-week follow-up visit.

Data may be captured in-person or remotely (e.g., entered directly into REDCap using a personalized coded link with no log-in required, verbally over the phone with a study team member, etc.), as applicable. Reminder phone calls, texts, and/or emails will be sent to participants at their preferred contact method indicated on the Intake CRF (Appendix B).

#### **Missed Appointments and Study Removal:**

If a participant misses a scheduled appointment, they will be contacted to reschedule in order to maintain the treatment plan of their assigned study treatment group. In the event that a participant misses an appointment, study staff will make one attempt to reschedule each day on three separate days (for three total attempts to reschedule). If the participant cannot be reached or does not respond/reschedule, they will be removed from the study due to non-compliance.

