## 11.0 Statistical/Data Analysis Plan

### 11.1 Statistical Considerations:

List the statistical methods to be used to address the primary and secondary objectives, specific aims, and/or research hypotheses. Explain how missing data and outliers will be handled in the analysis. The analysis plan should be consistent with the study objectives. Include any subgroup analyses (e.g., gender or age group). Specify statistical methods and variables for each analysis. Describe how confounding variables will be controlled in the data analysis

Descriptive statistics will report location and scale in terms of mean and standard deviation for normally distributed variables, median and interquartile intervals for ordinal metric variables, and in terms of proportion and size for categorical variables. Descriptive statistics will be reported for baseline demographic and clinical characteristics at an overall level and by initial treatment group.

Outliers will be removed if determined to be erroneous based on relevant clinical expertise. Confounding will be principally controlled by randomization. In regards to the treatment of missing data, Oura Ring data will be analyzed despite presence of missing data at any point; with regards to non-continuous outcomes, data will be analyzed only if baseline and the 3-week follow-up are both present. In the event of missing data for a mid-point follow up (i.e., not baseline or the 3-week follow up), said patient will still be included in all models.

Statistical analyses will use generalized additive models predicting the change in outcome measures at 3 weeks relative to baseline for all measures except Oura Ring data. Oura Ring data will be aggregated by averaging readings across each 24-hour period and will be modeled using multi-level models incorporating random effects. Sensitivity analyses will be performed on longitudinal data for each outcome metric and will include multi-level models incorporating random effects as well as control variables to account for any differences explained by a selection of patient characteristics (such as body weight, etc.).

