### 11.6 Data Analysis Plan: Complete description: Background, Objectives, Design, Step by Step how the project is going to be done, Data analysis plan:

Descriptive statistics will report location and scale in terms of mean and standard deviation for normally distributed variables, median and interquartile intervals for ordinal metric variables, and in terms of proportion and size for categorical variables. Descriptive statistics will be reported for baseline demographic and clinical characteristics at an overall level and by initial treatment group.

Statistical analyses will use generalized additive models predicting the change in outcome measures at 3 weeks relative to baseline for all measures except Oura Ring data. Oura Ring data will be aggregated by averaging readings across each 24-hour period and will be modeled using multi-level models incorporating random effects. Sensitivity analyses will be performed on longitudinal data for each outcome metric and will include multi-level models incorporating random effects as well as control variables to account for patient characteristics. Exact selection of control variables will be guided by observed differences within final collected data as well as relevant clinical expertise.

Hypothesis tests will be two-tailed and statistical significance will be considered at the putative threshold ( $\alpha=0.05$ ). Any secondary P-values will be subject to a false discovery rate adjustment in keeping with best statistical practices. Multilevel models will incorporate random effects to account for repeated measures, using distribution families and link functions appropriate for the outcomes of interest, determined using quantile-quantile (QQ) plots analyzed for best model fit. All statistical analyses will be performed using the R Programming language.

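### Removal after an unrescheduled missed appointment, with no outcome follow-up provided for, lets attendance after randomisation help decide who enters the 3-week analysis

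*Combined protocol and SAP*

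**What the plan says.** Section 10.1, Missed Appointments and Study Removal, applies to any scheduled appointment and refers to the assigned arm, so it operates after randomisation. After a miss, "study staff will make one attempt to reschedule each day on three separate days". Then: "If the participant cannot be reached or does not respond/reschedule, they will be removed from the study due to non-compliance".

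Under 3-Week Follow-Up in the same section, "Study participation will end after the completion of the 3-week follow-up visit". That part also says "Data may be captured in-person or remotely", but does not extend this to men already removed.

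Sections 11.1 and 11.6 give the main analysis as "generalized additive models predicting the change in outcome measures at 3 weeks relative to baseline for all measures except Oura Ring data". Section 11.1 adds that "with regards to non-continuous outcomes, data will be analyzed only if baseline and the 3-week follow-up are both present", and that where a mid-point follow-up is missing, "said patient will still be included in all models". Longitudinal multi-level models are planned as sensitivity analyses. No imputation is described. Grouping by assigned arm appears only for baseline tables: "Descriptive statistics will be reported for baseline demographic and clinical characteristics at an overall level and by initial treatment group".

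Three other places bear on the point:
- Section 10.1, Photobiomodulation Treatment, expects some sessions to be missed because of operational demands.
- Section 10.2, Appendix E, collects strength, Borg and Elloumi at the 3-week follow-up only. CMJ and the soreness VAS carry no such limit.
- Section 13.6 stops data collection after withdrawal by the participant. Its part on withdrawal without consent lists failure to adhere, but mentions later contact only to recover study materials.

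**The concern.** A change score needs a week-3 value. A man removed after week 1 or 2 for not rescheduling appears to have none, so what he did after randomisation takes him out of the main comparison. Section 10.1 (Sham PBMT Arm) attributes any group difference to PBMT, and section 11.1 relies mainly on randomisation to control confounding. Both need the analysed groups to stay close to the randomised ones.

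The outcomes include soreness, pain, fatigue and performance, any of which could affect attendance. If they do, the men who remain are selected on what is being measured. Apart from bias, a study that section 11.5 concedes may be underpowered would give up values it could have collected.

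**Working it through.** **The plan's own figures.** Section 11.2 assumes roughly 20% attrition and a final sample of 85.
- 85 / 0.8 = 106.25, so about 107 randomised and 107 − 85 = 22 lost (20.6%).
- The other 116 − 107 = 9 (7.8% of 116) are read here as the allowance for screen failures, although section 11.4 speaks of up to 116 randomised. The overall gap, 1 − 85/116 = 26.7%, is therefore not used as a loss rate.
- Section 11.5's power figures reproduce with a noncentral F test (noncentrality 0.15 × N, alpha 0.05) if 4 predictors are assumed: 80.3% at N = 85 and 90.1% at N = 108. The number of predictors is not stated. The sample size is not challenged here.
- As a yardstick, 42 and 43 men per arm can detect 0.615 SD (two-sample t test, two-sided 5%, 80% power).

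**How often the rule would act.** The documents give no rate. Assume independent unrescheduled misses with probability p = 1% to 2% per appointment, k appointments covered by the rule, and 107 men. The probability of at least one is 1 − (1 − p)^k.

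| Appointments that count | k | p = 1% | p = 2% |
|---|---|---|---|
| Two mid-point visits | 2 | 2.0% (2 men) | 4.0% (4 men) |
| Three follow-up visits | 3 | 3.0% (3 men) | 5.9% (6 men) |
| 9 sessions and 3 follow-up visits, counted separately | 12 | 11.4% (12 men) | 21.5% (23 men) |

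Clustering of misses within the same man would lower these. The top figure slightly exceeds the 22 losses planned for all causes. A man who misses the week-3 visit itself and never reschedules has no week-3 value under any rule, so only removals before that visit are avoidable. Many unreachable men would also be lost anyway.

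**Bias in the arm difference, simple formula.** Let gap be the mean outcome of removed minus retained men, taken as the same in both arms, and let p_active and p_sham be the proportions removed. The retained mean in an arm is the full mean minus p × gap, so bias (active minus sham) = gap × (p_sham − p_active). Sizes, with assumed inputs:
- Equal removal: gap × 0 = 0.
- 10-point difference, gap 0.5 SD: 0.5 × 0.10 = 0.05 SD.
- 20-point difference, gap 0.5 SD: 0.5 × 0.20 = 0.10 SD.
- 20-point difference, gap 0.8 SD: 0.8 × 0.20 = 0.16 SD.
- Overall removal of 2% to 6%, all in one arm: that arm loses about 4% to 12%, giving 0.5 × 0.04 = 0.02 SD to 0.8 × 0.12 = 0.096, about 0.10 SD.

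**Common outcome-driven mechanism, by simulation.** Assumptions: correlation between visits 0.6 to 0.8; true effect 0 or 0.5 SD, building linearly over 3 weeks; removal after week 1 or 2 with a logit slope of 1 per SD of the last observed change, the same in both arms. The completers' change-score bias is 0.000 when there is no true effect. With an effect of 0.5 SD it is −0.004 SD at 4% removal, −0.006 to −0.007 SD at 6%, and −0.016 to −0.018 SD at 20%.

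**Cross-check.** With 58 per arm, no true effect, and attendance correlated 0.2 to 0.5 with outcome, equal loss of 20% gives bias 0 and type I error 5.0%. Loss of 15% against 25% gives 0.03 to 0.08 SD and 5.2% to 6.5%. Loss of 10% against 30% gives 0.06 to 0.15 SD and 6.0% to 11.1%. Here too, harm needs unequal, outcome-related loss.

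**The case against.** **The rule may cost little.** Section 10.1 gives operational demands as the reason for missed sessions. Such absence need not relate to outcome, and inviting absent men back may recover few values. The contact procedure is fixed, participants are blinded, and sham is delivered in the same manner. This stands, and it is why the point is minor.

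**The plan already has safeguards.** Oura data are analysed despite gaps, completion status is recorded, and the longitudinal models can use weekly values collected before removal, if these are kept. This stands for CMJ and soreness. It does not help strength, Borg or Elloumi, which have no value between baseline and week 3.

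**Stronger readings that the documents do not support.**
- *Data collection is forbidden after removal.* The sentence in section 13.6 concerns withdrawal by the participant. For removal under section 10.1, loss of the week-3 value is inferred from the word removed and from the absence of any follow-up provision. The data collection schedule (Appendix K) was not available for this review.
- *The removal rule contradicts the tolerance of missed sessions and the mid-point rule in section 11.1.* Removal applies to men who cannot be reached or do not respond or reschedule, whereas the session text can describe reachable men held back by duty. Mid-point data can also be missing without removal. How the rules fit together is unclear, for example for a man who replies but cannot reschedule one session, but they are not flatly inconsistent.
- *The plan intends analysis by treatment received.* No section says so. An as-randomised set for outcomes is simply not stated.
- *The result would be biased towards PBMT.* Nothing shows unequal removal by arm, and the direction is unknown.

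**Conclusion.** The point holds as a minor one. A stated rule removes randomised men for non-attendance, no available section keeps their outcome assessments, and the main model for all but the Oura data needs the value they would then lack.

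The size is unknown from the documents and probably modest. The bias is about 0 with like removal, and about 0.02 SD or less under a common outcome-driven mechanism at up to 20% removal, against a detectable difference of 0.615 SD. It reaches 0.05 to 0.16 SD only with a 10 to 20 point imbalance and a 0.5 to 0.8 SD gap. These sizes, and the trigger range of 2% to 4% (two mid-point visits) up to 11% to 21.5% (all sessions and follow-ups), rest on assumed inputs. In a feasibility study with descriptive aims (sections 9.3 and 11.5), the case for change is that obtainable data are lost by rule and the repair is cheap, not that a material bias has been shown.

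A reader might infer that the multi-level model should become the main analysis. The material does not support that. The gain is about 0.02 SD or less under a common mechanism, and section 11.6 lets the control variables in those models be guided by the final data, so the change would bring that choice into the main comparison.

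**What to change.** 1. In sections 10.1 and 13.6, state that non-attendance alone does not end outcome collection. Unless they withdraw, such participants are still invited to the remaining weekly and 3-week assessments. Questionnaires can be collected remotely, as section 10.1 already allows; CMJ and strength need a visit.
2. Reconcile the removal rule with the session-attendance text in section 10.1, the mid-point rule in section 11.1 and the failure-to-adhere ground in section 13.6. No view is taken here on what the session rule should be.
3. In section 11.1, state that all randomised participants with outcome data are analysed in their assigned arm, and that missing week-3 values and their reasons are reported by arm.
4. Keep the 3-week change model as the main analysis and the longitudinal multi-level models as sensitivity analyses.

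The cost is a short amendment and a few extra final visits of about 25 minutes each (the length given in the recruitment brief). Keeping men who missed sessions may dilute the estimated effect somewhat.
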